# 7.9. Vital Signs, Physical Examinations, Clinical Laboratory Tests, Electrocardiograms, and Bone Mineral Density Measures

Section 6.10.1.10 details the requirements for measurement of safety parameters including vital signs, physical and gynecologic examinations, clinical laboratory tests, ECGs, and bone mineral density.

#### 7.10. Benefit/Risk Assessment

Adverse drug reactions (identified risks) associated with relugolix in women include nonserious events of hot flush, headache, hyperhidrosis, and loss of bone mineral density. In this protocol, relugolix will be evaluated for its benefit on endometriosis-associated pain. Low-dose hormonal add-back therapy with estradiol and norethindrone acetate will be evaluated for maintenance of bone mineral density during treatment with relugolix.

Potential risks that may be associated with relugolix treatment in women, based on nonclinical data and data available for similar compounds, include drug interactions, cardiovascular effects (QTc prolongation), hepatic enzyme increases, phospholipidosis, reproductive toxicity, and metabolic and cardiovascular changes (insulin resistance, dyslipidemia, increased weight) with an increased risk of diabetes mellitus and possible increased risk of cardiovascular disease. Additionally, there are potential risks associated with the addition of estradiol/norethindrone acetate. Summaries of findings from both nonclinical and clinical studies conducted with relugolix can be found in the current version of the Investigator Brochure.

The risk assessment and mitigation strategy for this protocol are outlined in Table 7-2.

Table 7-2 Protocol Risk Assessment and Mitigation Strategies

Potential Risk of Clinical Significance	Mitigation Strategy	
	Impact on Eligibility	Monitoring and Withdrawal Criteria
Bone Mineral Density Reversible loss of bone mineral density is a risk of the hypoestrogenic state induced by relugolix. This risk is mitigated by the co-administration of low-dose estradiol and norethindrone acetate hormonal add-back therapy.	Exclusion criteria for a history of osteoporosis, metabolic bone disease, and prior medical therapy for low bone mineral density.	Bone mineral density will be monitored per the Schedule of Activities and all fractures will be reported as adverse events.
Drug Interactions	Exclusion of co- administration of P-glyoprotein inhibitors/inducers.	Collection of adverse events.
QTc Prolongation Negative Thorough QT/QTc clinical study.	Empiric exclusion of baseline QTcF > 470 msec.	12-lead ECG will be monitored per the Schedule of Activities; withdrawal for QTcF > 500 msec.

Effective: 12-MAR-2018

Potential Risk of Clinical Significance	Mitigation Strategy	
	Impact on Eligibility	Monitoring and Withdrawal Criteria
Hepatic Enzymes Increase Isolated increases in hepatic transaminases have been observed in prior clinical studies. There have been no reported cases consistent with drug-induced liver injury including an increase in bilirubin. Abnormal liver function tests, also referred to as liver tests as these are not solely measuring liver function, are considered adverse events of clinical interest in this study.	Exclusion criteria for AST and ALT > 2 x the ULN; total bilirubin values > 1.5 x ULN	Abnormal liver tests (AST or ALT > 3 x ULN) that develop during the randomized study treatment period will be reported within 24 hours of study personnel awareness.
Phospholipidosis Data from nonclinical studies in rats and monkeys showed histopathological changes consistent with PLD. PLD by itself is not adverse. No clinical evidence of relugolix-related PLD-associated toxicity has been observed nor was there a clinically meaningful increase in a biomarker of PLD assessed in phase 2 clinical studies.	Patients with significant underlying medical conditions are excluded.	Routine safety monitoring including laboratory assessments, ECGs, and assessment of adverse events; visual acuity will be checked at the beginning and end of the study.
Metabolic Changes Metabolic changes (insulin resistance, dyslipidemia, and increased weight) with increased risk of diabetes are a potential risk of the hypoestrogenic state induced by relugolix.	Exclusion criteria for current medical history of cardiovascular disease.	Fasting lipids and glucose will be monitored during the study.
Reproductive Toxicity	Premenopausal compliance with specified acceptable nonhormonal contraception; exclusion of pregnant and lactating women.	Monthly pregnancy testing; immediate withdrawal for pregnancy.

Effective: 12-MAR-2018

Potential Risk of Clinical Significance	Mitigation Strategy	
	Impact on Eligibility	Monitoring and Withdrawal Criteria
Risk of Estradiol (1.0 mg)/Norethindrone Acetate (0.5 mg)  Low-dose estradiol and norethindrone acetate are approved for the prevention of postmenopausal osteoporosis and the treatment of moderate to severe vasomotor symptoms. It is contraindicated for women with a history of breast cancer or estrogen-dependent neoplasia, history of (or active) deep vein thrombosis, pulmonary embolism, thromboembolic disease (myocardial infarction or stroke within the past year), liver dysfunction, prior hypersensitivity, and pregnancy.	Women with breast cancer or other estrogen-dependent malignances, a history of deep vein thrombosis, pulmonary embolism, thromboembolic disease, liver dysfunction, prior hypersensitivity, and pregnancy are excluded. A mammogram, Papanicolaou test, physical examination, clinical chemistries, and 12-lead ECG will be performed prior to enrollment.	Clinical chemistries assessing liver function, fasting glucose and lipids, and urine pregnancy tests will be performed throughout the study. Adverse events will be recorded at each visit.

### 8. DATA QUALITY ASSURANCE

#### 8.1. Clinical Procedures

Sponsor personnel or designee(s) will visit the study site if necessary prior to initiation of the study to review information about the study drug, protocol requirements, eCRFs, monitoring requirements, reporting of serious adverse events, and to ensure a full understanding of the Study Reference Manual with the site personnel.

#### 8.2. Monitoring

This study will be monitored by the sponsor (or designee) in accordance with current Good Clinical Practice (GCP) regulations. By signing this protocol, the investigator grants permission to Myovant Sciences GmbH (or designee) and appropriate regulatory authorities to conduct onsite monitoring of all appropriate study documentation. In order to assure the accuracy of data collected in the eCRF, it is mandatory that representatives of the sponsor (or designee) have access to original source documents (eg, patient records, patient charts, and laboratory reports). During the review of these documents, the anonymity of the patient will be respected with strict adherence to professional standards of confidentiality. A study monitor will contact and visit the site regularly and will be allowed, on request at a mutually acceptable time, to inspect the various records of the study. It will be the study monitor's responsibility to inspect the eCRF at regular intervals throughout the study, to verify the adherence to the protocol and the completeness, correctness and accuracy of all eCRF entries, and to meet with the investigator to discuss study progress and compliance with the protocol and GCP. The study monitor should have access to

Effective: 12-MAR-2018

laboratory test results and any other source records and data needed to verify the entries on the eCRF. The investigator agrees to cooperate with the study monitor to ensure that any problems detected in the course of these monitoring visits are resolved. For this study, patient data will be entered into a sponsor-approved electronic database and combined with data provided from other sources in validated datasets then transmitted electronically to the sponsor (or designee).

Management of clinical data will be performed in accordance with applicable sponsor-approved standards and data cleaning procedures to ensure the integrity of the data (eg, removing errors and inconsistencies in the data).

Adverse events and concomitant medications terms will be coded using the Medical Dictionary for Regulatory Activities (MedDRA) and the World Health Organization Drug Dictionary Enhanced (WHO-DDE), respectively.

The investigator will retain original source documents and the sponsor will receive eCRFrequired data as electronic datasets. Patient initials will not be collected or transmitted to the sponsor.

#### 9. STATISTICAL CONSIDERATIONS AND DATA ANALYSES

A Statistical Analysis Plan will describe the detailed statistical methods and analyses for this study. The Statistical Analysis Plan will be prepared and finalized prior to unblinding of patients' study treatment assignments.

All hypothesis tests and confidence intervals will be 2-sided at an alpha level of 5%. Methodology to be used to maintain study-wide type I error rate of 5% across primary and secondary endpoint testing will be described in the Statistical Analysis Plan.

All efficacy and safety measures over the course of the study will be presented. Continuous data will be summarized by means, standard deviations, medians, maximum, minimum, and number of patients. Categorical data will be summarized by counts and percentages.

The study may be closed pending selected contingent safety procedures conducted after the last patient's Week 24/Early Termination or Follow-Up visit. After the study is closed, any pending required follow-up testing of bone mineral density or for menstruation recovery beyond the Follow-Up visit in patients not proceeding into the extension study will be captured and reported.

The single, final analysis of all efficacy and safety data will occur after approximately 600 patients have been randomized and have had the opportunity to be followed for 24 weeks of study treatment or through the 30-day safety follow-up visit (if not enrolling in the extension study, MVT-601-3103).

#### 9.1. **Randomization Methods**

Central randomization will be used and treatment allocation will be 1:1:1 to relugolix plus lowdose hormonal add-back therapy (Group A), relugolix monotherapy plus placebo followed by relugolix plus low-dose hormonal add-back therapy (Group B), and placebo (Group C) (see Table 5-3 for treatment group details). Randomization will be stratified by the following factors:

• Geographic Region: North America versus Rest of World; and

• Time since surgical diagnosis of endometriosis: < 5 years versus  $\ge 5$  years.

Statistical analyses for all efficacy endpoints will incorporate these stratification factors unless otherwise specified.

#### 9.2. Analysis Populations

The modified Intent-to-Treat (mITT) Population will consist of all patients randomized to treatment who have taken at least 1 dose of randomized study treatment. This will be the primary population used for the efficacy analysis.

The Per-Protocol Population will consist of those members of the mITT Population who have no relevant major protocol violations, defined as a subset of all major protocol violations (details will be provided in the Statistical Analysis Plan). The Per-Protocol Population will not be analyzed if this population comprises more than 95% or less than 50% of the mITT Population. This population will be used for confirmatory analysis of the primary efficacy endpoint. The Per-Protocol Population will be identified prior to unblinding the study treatment assignments.

The primary population for safety analyses will be the Safety Population, which will consist of all patients who are randomized and took at least 1 dose of randomized study drug treatment.

#### 9.3. Efficacy Analyses

Unless otherwise specified, efficacy analyses will be conducted using the mITT Population according to the randomized treatment assignment, and stratified analyses will be stratified by the randomization stratification factors. If the group of patients from any of the individual randomization stratification factors (eg, patients with a time from diagnosis of endometriosis < 5 years) comprises less than 10% of the entire mITT population, this stratification factor will be ignored for stratified analyses.

#### 9.3.1. Co-primary Efficacy Endpoints

The study has two co-primary efficacy endpoints comparing Group A versus Group C:

- Proportion of responders at Week 24/End of Treatment (EOT) pain assessment period, based on the dysmenorrhea NRS scores recorded in a daily electronic diary and use of rescue analgesics; and
- Proportion of responders at Week 24/EOT pain assessment period based on the NMPP NRS scores as recorded in a daily electronic diary and use of rescue analysesics.

A responder at Week 24/EOT is defined as a patient who had a reduction from Baseline of the determined threshold (or clinically meaningful difference) or greater from Baseline in pain and who did not have an increase in the use of rescue analgesic medications for endometriosis-associated pain during the Week 24/EOT pain assessment period compared with the use in the Baseline pain assessment period.

The Baseline pain assessment period is defined as the period from the date of the first dose of placebo in the Run-In Period through the day prior to the date of the first dose of randomized

Effective: 12-MAR-2018

study drug treatment The Week 24/EOT pain assessment period is defined as the last 35 calendar days immediately prior to and including the last dose of randomized study drug treatment.

Pain data collected in the Baseline pain assessment period will be used as baseline. The Baseline value for dysmenorrhea is defined as the mean NRS scores over the days with menses during the Baseline pain assessment period. The Baseline value for NMPP is defined as the mean NRS scores over the days without menses during the Baseline pain assessment period. The Baseline value for total dose counts is defined as the mean daily dose counts taken during the Baseline pain assessment period multiplied by 35.

The clinically meaningful difference will be determined for NMPP and dysmenorrhea separately (see the Statistical Analysis Plan for details). The anchor-based methods (using PGA for dysmenorrhea and PGA for NMPP as anchors) supplemented with both cumulative distribution function (CDF) and probability density function (PDF) curves will be considered as primary methods to derive the meaningful pain reduction thresholds to be used to define a responder.

Determination of the meaningful pain reduction threshold using PGIC as the anchor will also be explored as supportive.

A patient will be considered a non-responder if there is an increase in the use of rescue analgesic medications during the Week 24/EOT pain assessment period compared with the Baseline pain assessment period. Details will be provided in the Statistical Analysis Plan.

#### 9.3.1.1. **Primary Analysis**

The primary hypotheses for each of the co-primary efficacy endpoints to be tested in this study are the following:

1. Relugolix (Group A) is superior to placebo (Group C) with respect to proportion of responders at the Week 24/EOT pain assessment period based on the dysmenorrhea NRS scores recorded in a daily electronic diary and use of rescue analgesics:

Null hypothesis  $H_{01}$ :  $\pi^R \le \pi^P$  vs Alternative hypothesis  $H_{a1}$ :  $\pi^R > \pi^P$ 

2. Relugolix (Group A) is superior to placebo (Group C) with respect to proportion of responders at the Week 24/EOT pain assessment period based on the NMPP NRS scores recorded in a daily electronic diary and use of rescue analgesics:

Null hypothesis H02:  $\pi^R < \pi^P$  vs Alternative hypothesis Ha2:  $\pi^R > \pi^P$ where  $\pi^R$  and  $\pi^P$  are the responder rates for relugolix and placebo groups, respectively.

The co-primary endpoints of dysmenorrhea and NMPP responder rates will be evaluated using the mITT Population. A logistic regression model will be used to compare relugolix Group A with placebo Group C for each endpoint. The responder status will be the dependent variable; treatment will be the main effect, and Baseline pain scores and stratification factors will be the covariates. The study will be considered positive if both co-primary endpoints are statistically significant with 2-sided p-values < 0.05.

In addition, the difference in responder rates between Group A and C for each co-primary endpoint will be estimated and displayed along with their 2-sided 95% confidence intervals.

#### 9.3.1.2. Subgroup Analyses

Subgroup analyses of the co-primary efficacy endpoints comparing Group A versus Group C will be performed to determine whether treatment effects are consistent across clinically meaningful subgroups. The difference in responder rates and their 95% confidence intervals will be displayed in a forest plot. Subgroups will include but not be limited to the following: geographic region (North America, Rest of World) and time from diagnosis of endometriosis to study entry (< 5 years,  $\ge$  5 years) as well as other subgroups based on Baseline pain severity, age, and race. Details are provided in the Statistical Analysis Plan.

#### 9.3.1.3. Sample Size Justification

The following assumptions are used to determine the sample size for this study:

- 2-sided type I error rate: 0.05;
- Randomization: 1:1:1;
- Responder rate for Group C: 30-35%;
- Difference in responder rates between Group A and Group C: 20%;
- Dropout rate: 20%.

Assuming a dropout rate of 20%, approximately 200 women in relugolix Group A and 200 women in placebo Group C will provide at least 95% power at a 2-sided 0.05 significance level to detect a 20% difference in responder rates between Group A and Group C for each individual co-primary endpoint. This will provide an overall power of at least 90% for the study to detect a 20% treatment difference for both co-primary endpoints simultaneously. The responder rate for Group C is assumed to be between 30 and 35%. The proposed fixed sample size of 400 patients in Groups A and C is adequate to detect the target difference of 20% in responder rates between the two groups. It is calculated considering overall responder rates of close to 50% from which the maximum sample size is reached. With an additional 200 women in relugolix Group B, the total sample size will be approximately 600 women.

The assumed responder rate of 30 to 35% for Group C is within the range of responder rates (approximately 25 to 40%) observed in similar phase 3 endometriosis trials [Taylor, 2017]. The sample size and power calculations are based on the chi-squared test and were performed using the software package *nQuery* 4.0.0.0 (Statistical Solutions Ltd.).

### 9.3.2. Secondary Efficacy Endpoints

• Change from Baseline at Week 24/EOT in the EHP-30 Pain Domain scores in the relugolix 40 mg group co-administered with low-dose hormonal add-back therapy for 24 weeks versus placebo;

The change at Week 24/EOT from Baseline in EHP-30 Pain Domain comparing Group A and Group C is a key secondary endpoint to which Type 1 error protection will be extended.

Effective: 12-MAR-2018

To assist in score interpretation, a meaningful within-patient score change threshold for the EHP-30 pain domain will be determined using a similar approach as that for the primary endpoint. A responder at Week 24/EOT based on EHP-30 pain domain scores is defined as a patient who had a reduction of the determined threshold or greater from Baseline using PGA for function as the anchor. Proportion of responders at Week 24/EOT based on EHP-30 Pain Domain scores is a secondary endpoint;

The following secondary endpoints will be assessed comparing Group A with Group C. The Statistical Analysis Plan will specify to which additional secondary endpoints Type 1 error protection will be extended.

- Change from Baseline to Week 24/EOT in the mean dysmenorrhea NRS score;
- Change from Baseline to Week 24/EOT in the mean NMPP NRS score;
- Change from Baseline to Week 24/EOT in the severity scores on the PGA for dysmenorrhea
- Proportion of patients who are better or much better on the PGIC for dysmenorrhea at Week 24/EOT:
- Change from Baseline to Week 24/EOT in the severity scores on the PGA for NMPP.
- Proportion of patients who are better or much better on the PGIC for NMPP at Week 24/EOT;
- Change from Baseline to Week 24/EOT in the mean dyspareunia NRS scores.
- Proportion of patients who are better or much better on the PGIC for dyspareunia at Week 24/EOT;
- Change from Baseline to Week 24/EOT in the mean dyspareunia functional impairment on the sB&B scale:
- Change from Baseline to Week 24/EOT in severity scores on the PGA for pain;
- Proportion of responders at Week 24/EOT based on EHP-30 Pain Domain scores;
- Change from Baseline to Week 24/EOT in function impairment on the PGA for function;
- Change from Baseline to Week 24/EOT in each of the non-pain EHP-30 domains (Control and Powerlessness, Social Support, Emotional Well-Being, and Self-Image);
- Change from Baseline to Week 24/EOT in the mean dysmenorrhea functional impairment on the sB&B scale;
- Change from Baseline to Week 24/EOT in the mean NMPP functional impairment on the sB&B scale.

The following secondary endpoints will be assessed comparing Group B with Group C:

- Proportion of responders at the Week 24/EOT pain assessment period, based on their dysmenorrhea NRS scores recorded in a daily eDiary;
- Proportion of responders at the Week 24/EOT pain assessment period, based on their NMPP NRS scores recorded in a daily eDiary
- Change from Baseline at Week 24/EOT in the EHP-30 Pain Domain scores.
- Proportion of responders at Week 24/EOT based on EHP-30 Pain Domain scores.

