## Secondary Endpoints

The change at Week 24 from Baseline in EHP-30 Pain Domain comparing Group A and Group C is a key secondary endpoint to which Type 1 error protection will be extended. The Statistical Analysis Plan will specify to which additional secondary endpoints Type 1 error protection will be extended.

• Change from Baseline at Week 24 in the EHP-30 Pain Domain scores in the relugolix 40 mg group co-administered with low-dose hormonal add-back therapy for 24 weeks versus placebo;

The following secondary endpoints will be assessed comparing Group A with

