# Objectives Endpoints

### **Secondary Efficacy**

The secondary efficacy objectives and endpoints below are based on comparisons between Group A and Group C:

- To determine the benefit of relugolix 40 mg once daily co-administered with 24 weeks of low-dose estradiol and norethindrone acetate compared with placebo on function measured by the Endometriosis Health Profile (EHP)-30 Pain Domain.
- To determine the benefit of relugolix 40 mg once daily co-administered with 24 weeks of low-dose estradiol and norethindrone acetate compared with placebo on dysmenorrhea measured by the NRS.
- To determine the benefit of relugolix 40 mg once daily co-administered with 24 weeks of low-dose estradiol and norethindrone acetate compared with placebo on NMPP measured by the NRS.
- To determine the benefit of relugolix 40 mg once daily co-administered with 24 weeks of low-dose estradiol and norethindrone acetate compared with placebo on the Patient Global Assessment (PGA) for dysmenorrhea.
- To determine the benefit of relugolix 40 mg once daily co-administered with 24 weeks of low-dose estradiol and norethindrone acetate compared with placebo on the Patient Global Impression of Change (PGIC) for dysmenorrhea.
- To determine the benefit of relugolix 40 mg once daily co-administered with 24 weeks of low-dose estradiol and norethindrone acetate compared with placebo on the Patient Global Assessment (PGA) for NMPP
- To determine the benefit of relugolix 40 mg once daily co-administered with 24 weeks of low-dose estradiol and norethindrone acetate compared with placebo on the PGIC for NMPP.
- To determine the benefit of relugolix 40 mg once daily co-administered with 24 weeks of low-dose estradiol and norethindrone acetate compared with placebo on dyspareunia measured by the NRS.

- Change from Baseline at Week 24 in the EHP-30 Pain Domain scores.
- Change from Baseline to Week 24/EOT in the mean dysmenorrhea NRS score.
- Change from Baseline to Week 24/EOT in the mean NMPP NRS score.
- Change from Baseline to Week 24/EOT in the severity scores on the PGA for dysmenorrhea
- Proportion of patients who are better or much better on the PGIC for dysmenorrhea at Week 24/EOT.
- Change from Baseline to Week 24/EOT in the severity scores on the PGA for NMPP.
- Proportion of patients who are better or much better on the PGIC for NMPP at Week 24/EOT.
- Change from Baseline to Week 24/EOT in the mean dyspareunia NRS scores.

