#### 6.7. Early Termination Visit and Follow-Up Visit

Refer to the Schedule of Activities (see Section 1.1) for individual study visit procedures during the Early Termination visit and Follow-Up visit.

All patients withdrawing from the study prior to Week 24 will complete an Early Termination visit. The Early Termination visit procedures are identical to those of Week 24; however, for patients whose last dose of study drug is during Week 6 or earlier, the endometrial biopsy does not need to be performed. This procedure may be performed, however, at the investigator's discretion, if it aids in follow-up of an ongoing adverse event. The DXA is not required at the Early Termination visit in patients whose last dose of study drug was during Week 6 or earlier or within 4 weeks after completion of the Week 12 scan.

All patients who do not wish to or who are not eligible to enroll in the extension study (MVT-601-3103), will have a Follow-Up visit approximately 30 days after the last dose of study drug, or prior to the date of initiation of another investigational agent or hormonal therapy affecting the hypothalamic-pituitary-gonadal axis or surgical intervention for endometriosis, whichever occurs first. This visit will be used to assess safety after discontinuation of study treatment including adverse events, clinical safety laboratories, 12-lead ECG, and return of menstruation.

Patients who withdraw early from this study will undergo the Follow-Up visit approximately 30 days after the last dose of study drug, or the date of initiation of another investigational agent or hormonal therapy affecting the hypothalamic-pituitary-gonadal axis or surgical intervention for endometriosis, whichever occurs first.

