### 6.10.1.3. Patient eDiary

All women enrolled in the study will be provided with a device with an application for a patient eDiary (See Appendix 2), along with detailed instructions for its use. Patients will complete

Effective: 12-MAR-2018

daily eDiary entries including NRS pain scores, menstruation information, analgesic drug use, date and time of study drug administration, and sB&B scale scores.

The site should review the eDiary data at every visit.

### 6.10.1.4. Endometriosis Health Profile - 30

The EHP-30 is used to evaluate the functional impact and the quality of life of patients with endometriosis (see Appendix 4). Patients will complete the EHP-30 questionnaire at the site at the Baseline Day 1 visit, Week 12 visit, and Week 24 visit before other types of study procedures, such as blood draws and physical examinations, are performed. The EHP-30 will be completed on a tablet device at the study site.

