#### 9.3.2.1. Secondary Efficacy Endpoint Analyses

If the treatment effects for both co-primary endpoints are statistically significant each at 2-sided 0.05 alpha level, the key secondary endpoint of change from Baseline at Week 24 in the EHP-30 Pain Domain scores will be tested comparing the relugolix Group A versus placebo Group C at a 2-sided 0.05 alpha level. The comparison will be performed using a mixed model repeated measures approach with treatment, randomization stratification factors, and treatment by visit interaction included as fixed effects and baseline value included as a covariate and an unstructured covariance. The dependent variable (change from Baseline) for each patient at each visit will be calculated based on the visit windows specified in the Statistical Analysis Plan. Based on this model, the difference in least squares means of change from Baseline between the two groups and corresponding 95% CI and p-value will be presented at Week 24 comparing Group A with Group C.

If this key secondary endpoint is positive, additional secondary efficacy endpoints to which Type 1 error protection will be extended will be tested comparing Group A with Group C using a closed testing procedure to control the familywise error rate at a 2-sided alpha level of 0.05. The details of the closed testing procedure will be provided in the Statistical Analysis Plan, which will be finalized prior to unblinding the trial.

For endpoints evaluating the change from Baseline to Week 24/EOT, treatment comparisons will be performed using a mixed model repeated measures approach with treatment, randomization stratification factors, and treatment by visit interaction included as fixed effects and Baseline value included as a covariate. The dependent variable (change from Baseline) for each patient at each visit will be calculated based on visit windows specified in the final Statistical Analysis Plan. In addition, descriptive statistics will be provided by treatment group and by visit.

For endpoints evaluating proportions, treatment comparisons will be performed using a stratified Cochran-Mantel-Haenszel test.

The daily average sB&B scores for each patient during a specific pain assessment period will be on a continuous scale for the secondary endpoints involving sB&B items with the categories as follows: none = 0, mild = 1, moderate = 2, severe = 3.

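### Does the Week 24/EOT label in Section 9.3.2 leave the time point of the protected EHP-30 Pain Domain test open?

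*Protocol*

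**What the plan says.** Section 9.3.2 gives the Group A versus Group C EHP-30 Pain Domain endpoint twice at Week 24/EOT: once as a bullet, and once in the sentence that grants type I error protection, "The change at Week 24/EOT from Baseline in EHP-30 Pain Domain comparing Group A and Group C is a key secondary endpoint".

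Three other places drop EOT for the same comparison:

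- Synopsis, Secondary Endpoints: "The change at Week 24 from Baseline in EHP-30 Pain Domain comparing Group A and Group C is a key secondary endpoint".
- Section 3, endpoints table: "Change from Baseline at Week 24 in the EHP-30 Pain Domain scores".
- Section 9.3.2.1, test paragraph: "the key secondary endpoint of change from Baseline at Week 24 in the EHP-30 Pain Domain scores will be tested".

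For Group B versus Group C the label is Week 24/EOT in the synopsis, in Section 3 and in Section 9.3.2: "Change from Baseline at Week 24/EOT in the EHP-30 Pain Domain scores".

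The working definition of EOT is in Section 9.3.1 and concerns the diary: "The Week 24/EOT pain assessment period is defined as the last 35 calendar days immediately prior to" and including the last randomized dose. The EHP-30 is not a diary item. Section 6.10.1.4 has it completed on a tablet at the site "at the Baseline Day 1 visit, Week 12 visit, and Week 24 visit before other types of study procedures". Women who leave early also complete it, since Section 6.7 says: "The Early Termination visit procedures are identical to those of Week 24".

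**The concern.** This endpoint comes directly after the co-primaries, and every further protected secondary test depends on it. The sentence granting protection and the paragraph specifying the test carry different time labels. The protocol does not use the two labels loosely elsewhere: the synopsis and Section 3 keep this endpoint at Week 24 and put most of the other Group A versus Group C endpoints at Week 24/EOT.

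The diary definition of EOT cannot be carried over to a questionnaire given at three scheduled visits. A reader could therefore supply a meaning, namely the last available score, whether from Week 24 or from Early Termination. A woman who stops at Week 16 would then have her Early Termination score as her endpoint value. Under the Week 24 label she would be missing at Week 24 and handled by the repeated-measures model. Those are different targets and could give different estimates. If the protocol allowed both, the protected hypothesis would not be unique.

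**Working it through.** **Step 1. What Section 9.3.2.1 fixes for the protected test.**

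- Comparison: Group A versus Group C.
- Gate: both co-primaries significant at 2-sided 0.05.
- Level: 2-sided 0.05.
- Model: mixed model for repeated measures with treatment, stratification factors, treatment-by-visit interaction, the baseline value as covariate, and unstructured covariance.
- Result reported: difference in least squares means, 95% confidence interval and p-value at Week 24.

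Nothing in that list depends on a meaning of EOT.

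**Step 2. What Section 9.3.2.1 says for change endpoints labelled Week 24/EOT.** A later paragraph covers them. It again uses a mixed model for repeated measures with treatment, stratification factors, treatment-by-visit interaction and baseline. In both paragraphs the change is calculated per patient and per visit, using visit windows left to the SAP. Two differences are visible: only the first paragraph names the unstructured covariance, and only the first names the visit of the contrast. Neither paragraph contains a last-value rule. Even if the Section 9.3.2 label moved the endpoint into the second paragraph, an Early Termination score would still enter the model at the visit window in which it falls.

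**Step 3. Whether any other section supplies a substitution rule.** Section 9.3.1 defines the period for diary scores only. Section 6.7 and the combined Week 24/Early Termination column in the Schedule of Activities say what is collected, not how it is analysed. No section carries an Early Termination EHP-30 score forward to Week 24.

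**Step 4. How large the issue would be if such a rule existed.** Inputs from Section 9.3.1.3: 200 women per arm and 20% dropout.

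- Early leavers: 0.20 × 200 = 40 per arm, so 2 × 40 = 80 of the 400 in Groups A and C.
- Women with an observed Week 24 score: 200 − 40 = 160 per arm.

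The 40 is an upper bound. Women lost to follow-up leave no Early Termination score. A visit from Day 169 − 10 = 159 to Day 169 + 20 = 189 already lies in the scheduled Week 24 window.

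For the effect, assume that every early leaver supplies a score, that early leavers show a fraction f of the completers' difference, and that the Week 24 target equals the completers' difference. With dropout d, the last-score difference as a share of the Week 24 difference is 1 − d(1 − f):

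| d | f = 0 | f = 0.5 | f = 1 |
|---|---|---|---|
| 0.20 | 0.80 | 0.90 | 1.00 |
| 0.10 | 0.90 | 0.95 | 1.00 |

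The values of f, and d = 0.10, are assumptions; the protocol gives no EHP-30 effect or missingness figure. The table describes a rule that the protocol does not contain.

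**Step 5. Whether any stated design figure moves.** The protocol states power only for the co-primaries. With n = 160 evaluable per arm and the chi-squared test, power = Φ[(0.20√n − 1.96√(2p̄(1 − p̄))) / √(p₁(1 − p₁) + p₂(1 − p₂))].

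- 30% versus 50%: (2.530 − 1.358) / 0.678 = 1.728, power 95.8%; both endpoints under independence, 0.958² = 91.8%.
- 35% versus 55%: (2.530 − 1.379) / 0.689 = 1.670, power 95.3%; both endpoints 90.7%.

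These reproduce the stated minimum of 95% for each endpoint and 90% for both. The EHP-30 label enters none of them.

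**The case for a change.** The strongest case for a correction is that the protocol itself, not the SAP, states the time point in two ways, in current text and on an alpha-protected endpoint. An SAP author could cite Section 9.3.2 as authority for a last-score analysis. The schedule's combined Week 24/Early Termination column makes it easy to file an early score under Week 24. On this view the hypothesis should read the same wherever it appears.

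The mismatch stands, and so does the observation that EOT has no stated meaning for the EHP-30. The inference that the test is therefore undetermined does not stand. Section 9.3.2.1 is the operative text for the test and names the Week 24 contrast, and the synopsis and Section 3 agree with it. An author who substituted early scores would be adding a rule that the protocol does not state. The SAP must also be final before unblinding, so the label gives no opening for a choice made on unblinded results.

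The placement of Early Termination scores in visit windows, and the working meaning of EOT for a questionnaire, are details that a protocol commonly leaves to the SAP; Section 9.3.2.1 defers the windows to it expressly. An EOT definition would matter more for the EHP-30 responder endpoint, since the Cochran-Mantel-Haenszel test needs one status per woman. That is a different endpoint and does not bear on the protected change score. The Group B versus Group C label is consistent across the sections that state it, so there is no contradiction to resolve there.

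**Conclusion.** The inconsistency is real but clerical: two statements in Section 9.3.2 carry a label that the synopsis, Section 3 and Section 9.3.2.1 do not use for this comparison. An analyst following Section 9.3.2.1 arrives at one test, with the contrast at Week 24. The change endpoints labelled Week 24/EOT get the same by-visit type of model. Tidying the two labels would be an editorial matter that alters no estimate, p-value, alpha allocation, power or sample size. The figure of up to 80 women in 400 shows what a last-score rule would touch at 20% dropout; it does not measure an effect of the protocol as written.

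This conclusion rests on reading Section 9.3.2.1 as governing the test, and on the SAP, which is not at hand, setting ordinary visit windows as the protocol says it will. On that footing no change to the plan is needed.
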